### 9.1 Patient traceability

### 9.2 Data collection and retrieval

### 9.3 Publication of data

## 10.0 Estimated costs

## 11.0 Bibliography

## 1.0 Introduction

Benign prostatic hyperplasia (BPH) was treated with open surgery until the early 1980s. Over the last two decades, the therapeutic approach has undergone a marked change. Until the second half of the 1980s, the treatment of choice in most cases was trans-urethral treatment (TURP). During the 1990s the appearance of alpha-blocker drugs led many urologists to treat benign hyperplasia with a medical and non-surgical approach. Gradually the number of patients treated with TURP has been reduced in favor of medical therapy. At the same time there has been a growing interest in minimally invasive interventional therapies with the aim of finding a more effective therapy than the medical one and at the same time less aggressive than the trans-urethral treatment. The regional local diffusion of microwaves and other hyperthermic therapies have been used until the advent of the GreenLight PVP technique (green light laser) which has completely supplanted all other minimally invasive techniques. This type of method has many advantages over the traditional TURP technique, especially in patients on anticoagulant therapy. The green light laser technique also reduces the operating times and is very useful for the treatment of large glands that require the administration of considerable amounts of energy. The only study in which the efficacy of the percutaneous ablative treatment with transperineal neodymium laser of benign prostatic hypertrophy was evaluated was conducted by Patelli et. to (1) in 2017, which confirmed a significant volume reduction of the gland through exclusively imaging and clinical follow-up. Using thin needles (21G) a trans-perineal percutaneous approach is possible, with less invasiveness. Placing from two to four sources in the context of the gland based on its volume, it is possible, with applications of short duration, to obtain significant volume reductions of the glandular lobes themselves. Although the surgical approach is currently the most widely used option, mini-invasive surgery is rapidly spreading, representing in many cases the only possibility to intervene on patients for whom the psycho-physical conditions do not allow the surgical approach conventional or for which the extent of the lesion to be treated does not justify the risk of surgery (for example in geriatric patients or patients with BPH at the same time as a neoplastic disease of another site). With the availability of a minimally invasive technology, which guarantees the effectiveness of classical methods, a clear reduction in intervention and hospitalization costs and a reduction in social cost can also be achieved.

## 2.0 Objective of the study

With this we intend to evaluate the efficacy of the percutaneous ablative treatment with neodymium laser, that is the complete profile of safety and tolerability in acute and in the follow up, in patients suffering from Benign Prostatic Hypertrophy using, for the first time, as the main diagnostic tool in the follow-up multiparametric prostate MRI that allows us to evaluate with objective data the volume reduction of the glandular volume in the follow-up, any morphostructural gland changes and the correlation of the aforementioned advanced imaging data with the clinical data.

## 3.0 Design of the study

Non-pharmacological interventional study in which each patient constitutes self-control. The clinical evaluation will be carried out at three different times:

Time 1: eligibility assessment, signing of informed consent

Time 2: admission, laser ablation and control with multiparametric MRI of the post-procedural prostate (T0).

Time 3 Follow up at 3 (T1) -6 (T2) -12 (T3) months from the procedure.

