## 4.0 Materials and Methods

### 4.1 Selection of patients

Patients will be recruited by the Departments of Urology and Diagnostic Imaging of the University Hospital "Tor Vergata".

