#### 4.1.1 Inclusion criteria

- Age over 65 years
- Benign prostatic hypertrophy (confirmed by multiparametric prostate MRI to be performed pre-treatment)
- PSA value  $\leq 4$  ng / ml
- Indicative flow meter test for obstructive pathology
- Medium-high surgical risk.
- Presence of obstructive symptoms (voiding hesitation, intermittent mitto, reduction of urinary flow, incomplete emptying of the bladder, post-voiding incontinence and irritative symptoms such as urinary frequency, dysuria, nocturia - quantified with IPSS)
- Signature of the information sheet and of the informed consent to the treatment, to the execution of the multiparametric MRI and to the administration of the paramagnetic contrast medium.

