##### 5.2 Post-discharge follow-up

Specialist examination, suprapubic ultrasound of the urinary tract (with evaluation of the post-residual residue) and multiparametric prostate MRI at 3 months, 6 months and 12 months and subsequent checks according to clinical judgment.

A chemical-physical urine test and any urine culture should be attached to each clinical-ultrasound evaluation. At each reevaluation the IPSS form and the data collection form will be filled out.

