### 6.5 Sample

Since this is a pilot study, a statistical calculation of the sample size cannot be performed due to the lack of statistics for the purpose. 40 patients are expected to be enrolled in the study.

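### Does a stated study duration of 12 months conflict with a last visit 12 months after each patient's procedure?

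*Combined protocol and SAP*

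**What the plan says.** Section 7.0 consists of a heading for the duration of the study and the single entry of 12 months. It does not say whether this is follow-up per patient, the enrolment period or the whole study.

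The visit schedule is in two places. Section 3.0 has "Time 3 Follow up at 3 (T1) -6 (T2) -12 (T3) months from the procedure", preceded by "Time 1: eligibility assessment, signing of informed consent" and then by the admission for ablation. Section 5.2 asks for "multiparametric prostate MRI at 3 months, 6 months and 12 months and subsequent checks according to clinical judgment", and adds "At each reevaluation the IPSS form and the data collection form will be filled out".

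Recruitment still lies ahead: Section 4.1 has "Patients will be recruited by the Departments of Urology and Diagnostic Imaging", and Section 6.5 has "40 patients are expected to be enrolled in the study". The diagnosis must also be "confirmed by multiparametric prostate MRI to be performed pre-treatment" (Section 4.1.1). The available text gives no recruitment period, accrual rate or total study length.

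**The concern.** A heading about study duration is normally read as first patient in to last patient out. On that reading 12 months leaves no room for anything but the follow-up of patients treated on the first day. Screening takes time, and 40 patients will not all be treated at once.

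If the study really stopped at month 12, the 12-month visit would be almost empty. That would matter. Section 2.0 makes MRI during follow-up the main diagnostic tool, Section 6.4 plans a repeated-measures ANOVA, and no rule for missing visits is stated. The end of the study would also be unclear for the closure notice to the ethics committee (Section 8.2.2) and for the retention of documents (Sections 8.3 and 9).

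**Working it through.** **Inputs**
- Stated duration: 12 months (Section 7.0).
- Visits: T1, T2 and T3 at 3, 6 and 12 months after the procedure (Sections 3.0 and 5.2).
- Planned enrolment: 40 patients (Section 6.5).
- S, the first patient's time from consent to procedure: not given.
- A, the time from first to last procedure: not given.

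**Can the stated figure be reproduced?**

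Total from first consent to last T3 = S + A + 12.

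- As a whole-study length, this equals 12 only if S = A = 0, that is, all 40 patients treated at once with no screening time. The figure is not reproduced.
- As follow-up per patient, procedure to T3 = 12 months. The figure is reproduced exactly.
- As an enrolment window, A = 12 implies 40/12 = 3.3 patients per month and a total of 12 + 12 = 24 months plus S. Nothing in the documents excludes this.

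**How far beyond 12 months?** This needs an assumed A. The values below are illustrations only, with S = 0.

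| Assumed A (months) | Patients per month (40/A) | Total (A + 12, months) |
|---|---|---|
| 3 | 13.3 | 15 |
| 6 | 6.7 | 18 |
| 9 | 4.4 | 21 |
| 12 | 3.3 | 24 |

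**What would closure at month 12 cost?** A patient reaches a visit due F months after the procedure only if treated by month 12 − F: month 9 for T1, month 6 for T2, month 0 for T3. With even accrual over A months, the share reaching the visit is (12 − F)/A, capped at 1.
- A = 6: T2 share = 6/6 = 1, so all 40 reach T2.
- A = 9: T2 share = 6/9 = 0.67, about 27 of 40.
- A = 12: T2 share = 6/12 = 0.50, or 20 of 40; T1 share = 9/12 = 0.75, or 30 of 40.
- T3: share = 0/A = 0 for any A above zero.

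**Does the plan lead there?** No section orders closure at a calendar date. Sections 3.0 and 5.2 tie the visits to the patient's own course, and Section 5.2 foresees checks after month 12. Sections 8.2.2, 8.3 and 9 refer to closure or completion as an event, not as a month. The T3 loss therefore does not follow from the plan as written.

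**Does any analysis use the figure?** The primary endpoint (Section 6.1) names no time point. Section 6.4 does not mention study duration. Section 6.5 states that no sample size calculation was made. None of these changes under any of the three readings.

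**The case for a change.** The best case for a change is that the gap remains on every reading. If 12 months means the whole study, it is impossible; if it means follow-up per patient or enrolment, the label is loose and the total is missing. Simultaneous treatment is ruled out by the protocol's own figures: at the 30 minutes per treatment stated in Section 4.3, 40 treatments take 40 × 30 = 1,200 minutes, or 20 hours, before the MRI that follows each one. One rewritten line would cure this at almost no cost, and it would define completion for archiving and for the closure notice.

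Most of this is correct. Twelve months cannot run from first consent to last visit, and a recruitment period and total would be useful to whoever plans the work. What does not stand is the step to a harm. Lost T3 data require a calendar stop that nobody has ordered and that would contradict Sections 3.0 and 5.2. The rewritten line would also leave the recruitment period blank for the investigators to supply, so it would correct no number that the analysis uses.

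**Conclusion.** No change to the plan follows. Section 7.0 is imprecise. It cannot describe the whole study, whose length is 12 months plus screening plus accrual, but it agrees exactly with follow-up per patient, which is the most natural reading beside Sections 3.0 and 5.2. The size of the excess cannot be derived; the totals of 15 to 24 months rest on assumed accrual of 3 to 12 months with no screening time.

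Staff who follow the visit schedule will see every patient at 3, 6 and 12 months after the procedure whatever Section 7.0 was meant to say. The endpoint, the planned 40 patients and the analysis stay as they are. The conclusion assumes that the study is not closed at calendar month 12. Nothing in the available text suggests that it will be, and such a closure would depart from the protocol's own schedule. The missing recruitment period and total are administrative details that the investigators can supply without touching the statistics.

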## 4.0 Materials and Methods

### 4.1 Selection of patients

Patients will be recruited by the Departments of Urology and Diagnostic Imaging of the University Hospital "Tor Vergata".

#### 4.1.1 Inclusion criteria

- Age over 65 years
- Benign prostatic hypertrophy (confirmed by multiparametric prostate MRI to be performed pre-treatment)
- PSA value  $\leq 4$  ng / ml
- Indicative flow meter test for obstructive pathology
- Medium-high surgical risk.
- Presence of obstructive symptoms (voiding hesitation, intermittent mitto, reduction of urinary flow, incomplete emptying of the bladder, post-voiding incontinence and irritative symptoms such as urinary frequency, dysuria, nocturia - quantified with IPSS)
- Signature of the information sheet and of the informed consent to the treatment, to the execution of the multiparametric MRI and to the administration of the paramagnetic contrast medium.

#### 4.1.2 Exclusion criteria

- MR signs of malignancy confirmed by biopsy investigation
- Urethral stenosis
- Serious coagulation disorders
- Inadequate compliance
- Ischemic pathology in the previous six months
- Presence of pacemakers
- Active phase inflammatory pathology
- Presence of III dominant prostate lobe
- Contraindications to the execution of MRI (claustrophobia, auricular implants, metal prostheses and other contraindications included in the specific informed consent)
- Paramagnetic contrast medium allergy.
- Acute and / or chronic renal failure (GFR  $< 50$  mL / min and serum creatinine  $> 1.5$  mg / d)
- Not adequate understanding of the information sheet

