## 4.2 Pre-procedural evaluation

### 4.2.1 Pre-treatment instrumental clinical examinations

- Specialized clinical evaluation
- Urinary apparatus ultrasonography with evaluation of post-voiding residue
- Multiparametric prostate RM (Using conventional morphological sequences associated with DWI sequence and evaluation after administration of paramagnetic contrast agent administered intravenously)
- Urodynamic studies
- EKG

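### Read literally, the renal exclusion needs GFR below 50 and creatinine above 1.5 together, so some men with GFR below 50 pass it before contrast MRI

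*Combined protocol and SAP*

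**What the plan says.** The renal criterion is in section 4.1.2. It excludes "Acute and / or chronic renal failure" and follows this with a bracket giving two laboratory limits: GFR below 50 "mL / min and serum creatinine" above 1.5. The creatinine unit is printed as mg/d, read here as mg/dL. No GFR equation is named. Section 4.2.2 lists creatinine among the pre-treatment blood tests but does not list GFR.

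Other sections set the context:

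- Section 4.1.1 requires "Age over 65 years", and consent must extend "to the administration of the paramagnetic contrast medium".
- Section 4.1.1 also requires BPH to be "confirmed by multiparametric prostate MRI to be performed pre-treatment".
- Section 4.2.1 describes that scan as including "evaluation after administration of paramagnetic contrast agent administered intravenously". Contrast is therefore given while eligibility is still being established.
- Sections 5.1 and 5.2 repeat the multiparametric MRI right after the procedure and at 3, 6 and 12 months. Contrast at those scans is an inference from the word multiparametric; it is explicit only before treatment.

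No other visible section sets a numeric renal limit.

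**The concern.** Joined by *and*, the two limits exclude only men who meet both. Serum creatinine is a weak stand-in for GFR in older or lighter men, because the same creatinine corresponds to a lower estimated GFR as age rises and, under Cockcroft-Gault, as weight falls. Every patient here is over 65, so the case that escapes the rule (GFR below 50 with creatinine not above 1.5) is plausible.

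What is at stake is eligibility and the care taken before a contrast injection. The protocol's own GFR limit may not work by itself. With no equation named, two investigators could also classify the same man differently. No endpoint or analysis is involved.

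**Working it through.** The plan gives no figure to reproduce. The check has two parts: the logic of the rule, and whether the men it lets through can exist in this age group.

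**Logic**

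| GFR < 50 | Creatinine > 1.5 | Excluded under *and* | Excluded under *or* |
|---|---|---|---|
| no | no | no | no |
| no | yes | no | yes |
| yes | no | **no** | yes |
| yes | yes | yes | yes |

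The third row is the gap.

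**Inputs**

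From the protocol: the limits of 50 mL/min and 1.5, and age over 65. Assumed, because the documents do not give them: the equation (three standard ones are tried), weights of 60, 70, 80 and 90 kg, and height 170 cm.

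**Formulas for men**

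- Cockcroft-Gault: (140 − age) × kg / (72 × Cr), in mL/min.
- CKD-EPI 2021, Cr above 0.9: 142 × (Cr/0.9)^−1.200 × 0.9938^age, per 1.73 m².
- MDRD: 175 × Cr^−1.154 × age^−0.203, per 1.73 m².
- The last two are converted to mL/min, the protocol's unit, by × BSA/1.73, with Du Bois BSA = 0.007184 × kg^0.425 × cm^0.725. At 170 cm, BSA is 1.695, 1.810, 1.915 and 2.014 m² at the four weights.

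**GFR at creatinine 1.5, the highest value not excluded**

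Example, age 80 and 60 kg, Cockcroft-Gault: 60 × 60 / (72 × 1.5) = 3600/108 = 33.3. At age 80, CKD-EPI gives 46.8 per 1.73 m², and 46.8 × 1.695/1.73 = 45.8 mL/min at 60 kg. MDRD gives 45.0 per 1.73 m², which converts to 44.1 mL/min. At age 66 the values per 1.73 m² are 51.0 (CKD-EPI) and 46.8 (MDRD).

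| mL/min | 60 kg | 70 kg | 80 kg | 90 kg |
|---|---|---|---|---|
| Cockcroft-Gault, age 80 | 33.3 | 38.9 | 44.4 | 50.0 |
| CKD-EPI, age 80 | 45.8 | 48.9 | 51.8 | 54.4 |
| MDRD, age 80 | 44.1 | 47.1 | 49.9 | 52.4 |
| Cockcroft-Gault, age 66 | 41.1 | 48.0 | 54.8 | 61.7 |
| CKD-EPI, age 66 | 50.0 | 53.4 | 56.5 | 59.4 |
| MDRD, age 66 | 45.9 | 49.0 | 51.8 | 54.5 |

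**Creatinine band with GFR below 50 that passes the literal rule**

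Set each equation to 50 mL/min and solve for creatinine. For Cockcroft-Gault this is (140 − age) × kg / 3600; at age 80 and 60 kg, 60 × 60/3600 = 1.00. A band exists only where the solution is below 1.50.

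| | 60 kg | 70 kg | 80 kg | 90 kg |
|---|---|---|---|---|
| Cockcroft-Gault, age 80 | 1.00-1.50 | 1.17-1.50 | 1.33-1.50 | none |
| CKD-EPI, age 80 | 1.40-1.50 | 1.47-1.50 | none | none |
| MDRD, age 80 | 1.35-1.50 | 1.42-1.50 | 1.50 only | none |
| Cockcroft-Gault, age 66 | 1.23-1.50 | 1.44-1.50 | none | none |
| CKD-EPI, age 66 | essentially none | none | none | none |
| MDRD, age 66 | 1.39-1.50 | 1.47-1.50 | none | none |

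At age 80 and 60 or 70 kg, all three equations put some men below the protocol's own GFR limit while the literal rule lets them through.

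**The case against.** The strongest reply is that nobody would read the bracket this way. The excluded condition is renal failure and the bracket only glosses it. Two bullets earlier, the MRI contraindications are a bracketed list of alternatives that ends with *and*, and no one would require all of them. The text is visibly a rough translation, so a connective is weak evidence of intent. This has force, and *and* may well stand for *or*. Against it, the same line uses *and / or* where either condition suffices, although there it joins acute and chronic, not the two laboratory limits. The ambiguity stands either way, and rewording serves both readings.

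Second, other safeguards may catch these men: the clinical term renal failure itself, the "Specialized clinical evaluation" in section 4.2.1, and the "other contraindications included in the specific informed consent", whose content cannot be seen. Section 10.0 adds that the examinations belong to existing clinical activity, but that is a statement about cost and sets no renal check. These safeguards reduce the likely consequence. They do not make the written limit work.

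Third, no harm is shown. The protocol never says that the renal limit is there because of contrast, and the documents contain nothing on risk in this GFR range. That is correct, and it is why the point stays minor.

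**Conclusion.** The concern holds, as a minor point. Followed literally, section 4.1.2 lets some men past the protocol's own GFR limit before a scan with intravenous contrast. They are mainly lighter men, and the gap is widest at the older ages. The extent ranges from nothing (for example CKD-EPI at 80 kg or more, at either age) to the whole creatinine range 1.00-1.50 (Cockcroft-Gault, age 80, 60 kg).

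These figures rest on assumed equations, weights and height, and on reading the creatinine unit as mg/dL. The documents give no distribution of creatinine or weight, so the number affected among the 40 planned patients cannot be calculated and may be zero. Whether such a man would actually receive contrast also depends on clinical judgment and on the unseen consent form.

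**What to change.** Reword section 4.1.2 so that GFR below 50 mL/min excludes on its own. Name the equation, and state that GFR is calculated before the pre-treatment contrast MRI from the creatinine already collected under section 4.2.2.

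The simplest wording replaces *and* with *or* between the two limits and prints the creatinine unit as mg/dL. This also makes creatinine above 1.5 a stand-alone exclusion, which the contrast concern does not need. Keep it only if the sponsor intends it, because it would lose some heavier men with GFR of 50 or more. At age 66 and 90 kg, for instance, Cockcroft-Gault reaches 50 only at creatinine 74 × 90/3600 = 1.85.

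The cost is a one-line clarification with no new test. A few candidates with GFR below 50 may become ineligible and need replacing to reach 40. No endpoint or analysis changes.

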## 4.2 Pre-procedural evaluation

### 4.2.1 Pre-treatment instrumental clinical examinations

- Specialized clinical evaluation
- Urinary apparatus ultrasonography with evaluation of post-voiding residue
- Multiparametric prostate RM (Using conventional morphological sequences associated with DWI sequence and evaluation after administration of paramagnetic contrast agent administered intravenously)
- Urodynamic studies
- EKG

#### 4.2.2 Pre-treatment blood chemistry tests

- Total and fractionated PSA
- CBC with platelet count and leukocyte formula -PT, PTT, INR
- Urine analysis and Urine culture
- Azotemia
- Creatinine

#### 4.3 Technique of performing a percutaneous laser ablation treatment

The treatments will be performed by the radiology team, on an outpatient basis using the supplied Echolaser XVG combined system. The procedure will be performed with the patient in gynecological position, and in safe conditions according to the current legislation for laser treatments (such as protective glasses). Treatment includes local anesthesia of the perineal region, under ultrasound guidance. At the discretion of the medical team, sedation can be carried out with anesthetic assistance. 2 or 4 needles of 21G, 1 or 2 will be inserted in the right bumper, 1 or 2 in the left bumper. In each needle a 300 micron optical fiber will be inserted - Ditta Elesta s.r.l. - [name] - Italy, at a distance of 8-10 mm from the urethra. For each lighting, for about 6 minutes, an energy of 1800 J per fiber will be delivered, at the power of 2-3 Watts. At the end the needle and the fiber will be retracted for about 1 cm ("pull-back"). Further lighting will follow, with delivery and duration and power equal to the previous one. Depending on the size of the middle lobe one or more pull-backs can be made. In total the treatment will consist in the delivery up to 3600 J, to the power of 2-3 W for a total duration of 30 minutes. The laser causes hyperthermia, denaturation and coagulative necrosis of proteins. The maximum volume treated in a session and the extent of the ablation vary according to the prostatic volume, anatomy and receptivity of the tissue. At the end of the treatment 20 mg of Urbason ev (if not specifically contraindicated by the patient) will be administered, for anti-edema and anti-inflammatory purposes. An antibiotic, pain relief and gastroprotective therapy will also be established for 1 week. After an adequate observation period, the patient will be discharged.

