### 9.2 Data collection and retrieval

Patient data will be collected in the data collection form during the clinical evaluation and in the follow up.

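### Section 4.3: the duration, power and energy stated for each laser illumination cannot all be right

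*Combined protocol and SAP*

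**What the plan says.** The protocol describes the treatment in section 4.3. For each illumination it gives a duration, an energy and a power: "For each lighting, for about 6 minutes, an energy of 1800 J per fiber will be delivered, at the power of 2-3 Watts". The needle and fibre are then withdrawn by about 1 cm, and "Further lighting will follow, with delivery and duration and power equal to the previous one". More than one withdrawal is allowed: "Depending on the size of the middle lobe one or more pull-backs can be made". The number of fibres varies: "2 or 4 needles of 21G, 1 or 2 will be inserted in the right bumper", with the same choice on the left and one fibre in each needle. The Introduction (1.0) likewise allows two to four sources, depending on gland volume. The section closes with a total: "delivery up to 3600 J, to the power of 2-3 W for a total duration of 30 minutes". It does not say whether that total is per fibre or per patient, or whether the 30 minutes is laser-on time or procedure time. No other section restates or corrects these figures.

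**The concern.** Any two of power, time and energy fix the third. The dosing sentence gives all three, and they do not fit together. The next sentence carries the mismatch into every later illumination by requiring the same energy, duration and power.

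Delivered energy is the dose of the only treatment in a single-group study, and the fibre lies 8-10 mm from the urethra. An operator who stops at about 6 minutes gives roughly half the energy of one who stops at 1800 J, and both can claim to have followed section 4.3. A report that repeats the section would state a dose that its own power and time do not produce. What is at stake is the clarity of the instruction and the reproducibility of the procedure.

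**Working it through.** **Inputs, all from section 4.3.** Power 2-3 W (stated twice); duration about 6 minutes (360 s); energy 1800 J per fibre per illumination; 2 or 4 fibres; an initial illumination plus at least one more after pull-back; total up to 3600 J; total duration 30 minutes.

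**Formula.** Energy (J) = power (W) × time (s), so minutes = J / (60 × W).

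**1. Attempt to reproduce 1800 J per fibre.**
- 2 W × 360 s = 720 J, and 720/1800 = 40%.
- 3 W × 360 s = 1080 J, and 1080/1800 = 60%.

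The stated energy is 1800/1080 = 1.67 to 1800/720 = 2.5 times what the stated power and time deliver. It is not reproduced.

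**2. What would be needed for 1800 J.**
- At 3 W: 1800/(60 × 3) = 10 minutes.
- At 2 W: 1800/(60 × 2) = 15 minutes.
- In 6 minutes: 1800/360 = 5 W, outside the stated range.

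The word *about* does not close the gap: even 9 minutes at 3 W gives 3 × 540 = 1620 J. Adding two fibres at 2.5 W gives 2 × 2.5 × 360 = 1800 J, but the text gives that energy per fibre.

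**3. Does the 3600 J total fit?** Per fibre with one pull-back, yes: 2 × 1800 = 3600 J. At 3 W this takes 3600/(60 × 3) = 20 minutes and at 2 W 3600/(60 × 2) = 30 minutes. The upper end equals the stated total duration. On this reading four figures agree (1800 J, 2-3 W, 3600 J, 30 minutes) and only the 6 minutes is out of line. The match assumes that the 30 minutes is laser-on time and that the fibres fire together; the section states neither.

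**4. Can 3600 J be a per-patient total?** Not at 1800 J per fibre per illumination with one pull-back:
- 2 fibres × 2 illuminations × 1800 = 7200 J.
- 4 fibres × 2 illuminations × 1800 = 14400 J.

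Two fibres with a single illumination would give 3600 J, but the section says that a further illumination follows. Even per fibre, a second pull-back gives 3 × 1800 = 5400 J, above the maximum.

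**5. A reading that keeps the 6 minutes.** Assume mid-range power of 2.5 W. Each illumination then gives 2.5 × 360 = 900 J; two give 1800 J per fibre (1440-2160 J over 2-3 W) in 12 minutes; two fibres give 3600 J per patient. This requires 1800 J to be the fibre total, against the wording of the sentence. It also fits two fibres only, since four would give 4 × 1800 = 7200 J.

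**The case against.** The strongest reply is that the section is workable in practice. Energy is the stated deliverable and the time is only approximate, so stopping at 1800 J is the natural reading. One radiology team treats 40 patients recruited at one hospital, so different sites cannot diverge. The operator who stops at 6 minutes is hypothetical. The endpoints and statistical analysis (6.1, 6.2 and 6.4) make no use of delivered energy. Most of this stands, and it limits how serious the point is. It does not remove the mismatch, because section 4.3 never says that energy ends an illumination.

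Two stronger readings are tempting, and the documents support neither. A reader might infer that the 1800 J is the error. The text shows only that three figures conflict, and the per-fibre reading in step 3 points to the duration instead. A reader might also infer that the 3600 J has no basis. It has one: two equal illuminations of 1800 J on one fibre, which is also 2 W for 30 minutes. What is missing is its unit, and its consistency with the fibres and pull-backs allowed.

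**Conclusion.** The dosing sentence is wrong as written. Per fibre and per illumination, the stated power and time give 720-1080 J against 1800 J stated, a 1.7- to 2.5-fold discrepancy. This rests only on energy being power multiplied by time and needs no outside assumption.

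The evidence within the section favours 6 minutes as the stray figure, with 10-15 minutes intended. This is not proven, because the 30 minutes may be procedure time. The 3600 J maximum is coherent per fibre with exactly one pull-back. At 1800 J per fibre per illumination it is not coherent per patient once the described pull-back is made, and a second pull-back exceeds it even per fibre.

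The sponsor should fix this, but it does not threaten the trial's conclusions: sample size and planned analyses are untouched. Nor do the documents show that any patient would receive a wrong dose.

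**What to change.** Before the first patient, the sponsor should amend section 4.3 to:

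1. Correct whichever figure is wrong, so that minutes = J / (60 × W) for each illumination. If 1800 J and 2-3 W are intended, replace the 6 minutes with 10-15 minutes (10 at 3 W, 15 at 2 W).
2. State that delivered energy ends each illumination, if that is the intent.
3. State whether 3600 J is per fibre or per patient, and make the permitted fibres and pull-backs consistent with it. Per fibre at 1800 J per illumination, that means one pull-back only, or a higher maximum.

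It would help to say in the same edit whether the 30 minutes is laser-on or procedure time. Delivered energy per fibre could also be recorded on the form named in section 9.2, if it is not already there; the form is not among the documents.

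The cost is a text correction and at most one line on a form. Sample size, visits and analysis do not change.
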